## Specific Aims

Platelet transfusion is commonly provided early after injury in patients with traumatic brain injury (TBI) to reverse antiplatelet medications (aspirin, Plavix). Taking antiplatelet medications potentially worsens intra-cranial hemorrhage and outcomes following TBI. Importantly, other antiplatelet medications such as NSAIDs have also been shown to inhibit platelet aggregation and compromise coagulation at doses commonly taken by warfighters. Whether current standard care room temperature (RT) platelet transfusion adequately reverses platelet inhibition and improves outcomes following traumatic brain injury remains poorly characterized. Cold stored platelets may provide better hemostatic correction and improve outcomes in patients with TBI requiring platelet transfusion.

Platelet use in far forward environments are not available due to logistical storage and shelf-life requirements. Cold-stored platelets can be refrigerated like red blood cells and plasma units and may be less prone to bacterial contamination. Growing evidence suggests that cold-stored platelets have superior hemostatic capabilities. For patients with brain injury, cold stored platelets may be beneficial in an urgent release fashion soon after arrival to the trauma center as compared to current standard care. Currently there is no high-level clinical trial evidence demonstrating the safety and efficacy of urgent release cold stored platelet transfusion following injury. The aims of the Cold Stored Platelet early intervention TBI (CriSP-TBI) pilot trial are to determine the feasibility, efficacy and safety of urgent release cold stored platelets in patients with traumatic brain injury requiring platelet transfusion.

**AIM#1:** Determine the feasibility, most appropriate study population and primary outcome that will lead to a large multicenter clinical trial designed to evaluate the effectiveness of cold stored platelet early intervention in patients with TBI requiring platelet transfusion.

**AIM#2:** Determine whether early cold stored platelet transfusion compared to standard platelet transfusion results in improved hemostatic function and clinical outcomes in patients with traumatic brain injury requiring platelet transfusion.

**AIM#3:** Determine if early cold stored platelet hemostatic function is similar at 1 through 7 days as compared to 8 through 14 days in patients with TBI on antiplatelet therapy.

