## Outcomes

**Primary Outcome:** The primary outcome for this pilot trial will be feasibility. Secondary performance and feasibility outcomes will include the proportion of eligible patients that can be randomized, 2) the proportion of eligible patients who are enrolled in the trial, 3) proportion of enrolled patients which adherence to the study protocol, and 4) proportion of enrolled patients who complete study follow-up.

**Secondary Outcomes:** Our principle secondary clinical outcome for the proposal will be 6-month Extended Glasgow Outcome Scale (GOS-E). Additional secondary outcomes will include 24-hour mortality, in-hospital mortality, need for craniectomy/craniotomy, need for ICP monitoring, TBI progression based upon serial CT imaging in initial 24 hours, Galveston Orientation and Amnesia Test (GOAT score) at discharge, incidence of allergic/transfusion reaction, incidence of transfusion related acute lung injury (TRALI), measurements of platelet hemostatic function, and incidence of thromboembolic events.

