**Platelet Hemostatic Function:** Once randomized, blood sampling for platelet hemostatic function prior to platelet transfusion irrespective of arm assignment will be performed if clinically feasible. Following each platelet transfusion, further assessment of platelet hemostatic function may be performed (up to 2 times). Platelet hemostatic function will be assessed by TEG analysis and TEG with platelet mapping. Whole blood aggregometry and flow cytometry will be performed when feasible across both arms.

**Thromboembolic events:** Pulmonary embolism, venous thrombosis, or arterial thrombosis that occurs during the primary admission hospital stay will be documented for all enrolled patients. Radiographic confirmation via CT imaging, transthoracic or trans-

esophageal echo, or ventilation/perfusion scanning will be required. Presumed or clinical suspicion for an embolic event that is unable to be verified radiographically will also be documented.

**Severity Stratification:** TBI characteristics will be recorded and based upon CT imaging results (classification: subarachnoid, subdural, intracerebral hemorrhage, epidural, +/- shift, multifocal) and TBI severity will be characterized by presenting GCS, Abbreviated Injury Severity (AIS) coding and Rotterdam CT scores.

**Predefined Subgroups:** Predefined subset analyses for the TBI cohort will be performed looking at 1) patients who did or did not receive a craniectomy/craniotomy, 2) patients who did or did not require ICP monitoring, 3) patients arrived from the scene of injury versus those brought from a referral hospital; 4) patients with a pre-injury history of aspirin use as compared to clopidogrel use; 5) CSPs with shelf time of 1 to 7 days as compared to 8 to 14 days. It is recognized that the study is not appropriately powered for these subgroup comparisons and the results and conclusions formulated from these subgroup analyses will be considered exploratory in nature and will not be used as a basis for treatment recommendations.

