A two-sided Chi-square test will be used to compare the distribution of the GOS-E between the treatment arms. An ordinal polytomous regression model will then be used to assess the independent impact of CSP on GOS-E after controlling for potential confounding effects of baseline characteristics which reveal imbalance between treatment groups. The analytic approach for the secondary trial outcomes will vary based on the type of outcome. For binary outcomes, a two-sided Chi-square test for proportions will be used to compare the proportions between those receiving and not receiving CSP. A logistics regression model will then be used to assess the independent impact of CSP on the secondary trial outcomes while adjusting for baseline GCS. For time-to-event outcomes (e.g., time to death), Kaplan-Meier curves will be generated for each treatment group and a log-rank test will be used to compare the distribution of the cumulative proportion. A Cox-proportional hazards regression model will be used to assess the independent impact of CSP on time to death after controlling for baseline GCS. For continuous outcomes a two-sided t-test for means will be used to compare the means between those receiving and not receiving CSP. An analysis of covariance model will be used to assess the independent effect of CSP. after controlling for baseline GCS .

Analyses to test for the homogeneity of the treatment effect will be carried out for the pre-defined subgroups. Regression models appropriate for the outcome variable (e.g., logistic regression for binary outcome variables) will stratified by the pre-defined subgroups. Estimate of the treatment effect (odds ratio) and 95% confidence interval will be generated for each model and displayed on a forest plot.

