Secondary analyses will be conducted to assess the impact of age of the CSP on outcomes. These analyses will be carried out among those who are randomly assigned to the CSP group and the impact of the age of the CSP on outcomes will be evaluated. Since the sample will not be randomly assigned, it will be important to adjust for potential confounding effects. A propensity score will be generated as an indicator of the age of the CSP ( $\leq 7$  days vs.  $> 7$  days). Multivariable regression models will be used to assess the independent relationship of age of the CSP on outcome. The model type will vary based on the outcome (e.g., logistic regression for binary variables). Each model will include a fixed main effect for the indicator of the age of the CSP as well as an inverse probability weight for the propensity of getting CSP  $\leq 7$  days of age.

**Sample Size Justification and Power Analysis (n=100):** For the enrollment, adherence and event rates needed for planning and feasibility analyses, we calculated the two-sided 95% CI for proportions ranging from 0.70 to 0.90. For example, a sample size of 100 produces a two-sided 95% CI of 0.82 to 0.95 when the sample proportion is 0.90. When the sample proportion is .70, the two-sided CI is 0.60 to 0.82. These confidence intervals are then repeated within the treatment arm.

Sample Size	Width	Proportion (P)	Lower Limit	Upper Limit
Full Sample				
100	0.19	0.700	0.60	0.82
100	0.17	0.800	0.71	0.87
100	0.13	0.900	0.82	0.95

One Treatment Arm				
50	0.27	0.700	0.55	0.82
50	0.24	0.800	0.66	0.90
50	0.19	0.900	0.78	0.97

For the principle secondary clinical outcome of the GOSE, based on a 2x8 (treatment x GOSE) there is 80% power to detect an effect size of 0.3788, assuming a type I error rate of 0.05, a two-sided alternative hypothesis, 7 degrees of freedom, and a sample size of 50 participants per treatment group.

**Randomization of Ineligible Participants:** It is anticipated that there will be a small proportion of patients enrolled who receive CSPs or standard care that in retrospect will not have met the entry criteria and are thus ineligible. In this circumstance, patients will be analyzed according to the group to which they were randomized. Subgroup analyses based on eligibility criteria will be performed if the number of patients so affected is large.

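### The planned model for platelet hemostatic function (Aim 2) names baseline GCS as its only covariate and leaves out the pre-transfusion value of the same assay, giving up precision if the two values are correlated

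*Combined protocol and SAP*

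**What the plan says.** Aim 2, under Specific Aims, is to "Determine whether early cold stored platelet transfusion compared to standard platelet transfusion results in improved hemostatic function and clinical outcomes". The Secondary Outcomes paragraph lists "measurements of platelet hemostatic function" among the additional secondary outcomes, behind the primary outcome (feasibility) and the principal secondary outcome (6-month GOS-E).

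The Platelet Hemostatic Function definition provides for a baseline: "Once randomized, blood sampling for platelet hemostatic function prior to platelet transfusion irrespective of arm assignment will be performed if clinically feasible". Assessments after transfusion are optional, at most two per patient. The assays are TEG and TEG with platelet mapping; in addition, "Whole blood aggregometry and flow cytometry will be performed when feasible across both arms".

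Under Analysis for Clinical Outcomes, one rule covers all continuous outcomes. The first step is unadjusted: "For continuous outcomes a two-sided t-test for means will be used to compare the means between those receiving and not receiving CSP". The second is adjusted: "An analysis of covariance model will be used to assess the independent effect of CSP. after controlling for baseline GCS". Nothing there is specific to platelet function. No change-from-baseline or repeated-measures analysis is described, and the plan does not say which post-transfusion value is analysed.

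Two other models have covariates that are not listed: the GOS-E regression, which adjusts for baseline characteristics found to be imbalanced, and the propensity score in the shelf-age analysis. Neither is the between-arm comparison of hemostatic function.

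**The concern.** GCS describes neurological state, while the outcome is a laboratory measure of platelet function. Patients can enter through antiplatelet use before injury or through a need for platelet transfusion, so their platelet function before transfusion plausibly differs a good deal. The same assay's pre-transfusion value is the natural covariate. It is drawn after randomisation but before transfusion, so the assigned product cannot have changed it.

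If that value is left out, the between-patient variation it would explain stays in the error term and the confidence interval is wider than it needs to be. There are at most 50 patients per arm, and fewer where sampling was not feasible. Aim 1 asks the pilot to help choose the outcome for a larger trial, so the precision of this estimate has practical use.

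**Working it through.** **The plan's own figure.** The only power statement is for GOSE: 80% at effect size 0.3788, 7 degrees of freedom, 50 per arm, two-sided 0.05. The noncentrality is 100 × 0.3788² = 14.35, and the noncentral chi-square gives power 79.995%, so the figure reproduces. There is no corresponding figure for platelet function.

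**Inputs.** From the documents: 50 per arm, 1:1 allocation, and a two-sided 0.05 level carried over from the GOSE calculation. Assumed, because the documents do not give them: correlation ρ between pre- and post-value (given arm and GCS) of 0.3, 0.5 or 0.7; a true difference of 0.5 SD (SD given GCS); complete post-values; and a fraction m = 0.3 of pre-values missing at random.

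**Formulas.** With a missing pre-value filled and the patient kept, residual variance is 1 for the fraction m and 1 − ρ² for the rest, so relative to the GCS-only model:

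- variance factor F = m + (1 − m)(1 − ρ²) = 1 − (1 − m)ρ²
- SE = √(2F/50), in SD units
- power = Φ(0.5/SE − 1.96)

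**GCS-only.** F = 1, SE = √(2/50) = 0.200, power = Φ(2.50 − 1.96) = 70.5%.

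**With the pre-value added.**

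| ρ | F | SE | Fall in SE | Power | Equivalent n per arm (50/F) |
|---|---|---|---|---|---|
| 0.3 | 1 − 0.7 × 0.09 = 0.937 | 0.194 | 3.2% | 73.3% | 53 |
| 0.5 | 1 − 0.7 × 0.25 = 0.825 | 0.182 | 9.2% | 78.6% | 61 |
| 0.7 | 1 − 0.7 × 0.49 = 0.657 | 0.162 | 18.9% | 87.0% | 76 |

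**Simulation check** (6,000 trials per setting, t tests, GCS included but unrelated to the assay, pooled-mean fill plus missing indicator). With the same inputs, GCS-only power was 69.4%, 69.5% and 68.7%; with the pre-value it was 71.1%, 76.1% and 84.9%. The gains are slightly smaller than in the closed form. With 30% of post-values also missing at random, power went from 53.5%, 54.9% and 54.0% to 55.0%, 60.8% and 70.1%.

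**Dropping patients without a pre-value.** In a complete-case analysis with a fraction f of pre-values observed, the SE ratio is √((1 − ρ²)/f). The gain disappears once f falls below 1 − ρ², which is 0.91, 0.75 and 0.51. At f = 0.7 and ρ = 0.5 the ratio is √(0.75/0.7) = 1.035, worse than the GCS-only model. How missing baselines are handled therefore matters.

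**Bias when values are not missing at random.** These runs have no true effect. One mechanism is applied first to pre-values and then to post-values: 20% missing at random in the standard arm, and about 40% missing in the CSP arm, rising with the pre-value (log odds 1 per SD). Nothing in the documents says that missingness behaves this way.

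| Values missing by arm and pre-value | GCS-only bias (SD), ρ = 0.3, 0.5, 0.7 | Adjusted bias (SD) |
|---|---|---|
| Pre-values; post-values complete | about 0.00 at each | 0.04, 0.07, 0.10 (indicator method) |
| Post-values; pre-values complete | −0.10, −0.17, −0.23 | 0.00 at each |
| Post-values; 30% of pre-values missing at random | as in the row above | −0.03, −0.05, −0.07 |

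If missing post-values depend on arm and on the post-value itself, neither model is safe: about −0.33 SD for GCS-only, and −0.30, −0.26 and −0.18 SD adjusted with complete pre-values.

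**The case against.** The strongest reply is that the size of the loss is unknown and may be trivial. No correlation is given. The treatment is meant to reverse platelet inhibition, so a strong link between pre- and post-values cannot be presumed. At 0.3 the gain is only two to three power points. Hemostatic function is one of many additional secondary outcomes in a feasibility pilot, and no power is claimed for it. All of this stands, and it limits the point to an inexpensive improvement.

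A second reply is that the remedy can do harm. The pre-sample is taken after open-label randomisation and only if feasible. If missing pre-values depend on arm and pre-value together, the missing-indicator model is biased while the planned GCS-only model with complete post-values is not. That also stands, and is why the planned model should stay in view. The reverse holds when post-values are missing by arm and pre-value: adjustment then reduces bias.

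Two stronger readings are tempting, and the documents support neither:

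- **That the pre-value is excluded from every model.** The propensity-score covariates in the shelf-age analysis and the imbalance-based covariates for GOS-E are not listed, so one can say only that no model names it.
- **That the GCS-only comparison is biased or inflates type I error.** Post-sampling is optional and treating physicians are unmasked, so differential missingness is possible. But no passage links missing samples to arm or to the assay value, and the VerifyNow results that may prompt a second unit are not among the assays listed in the platelet hemostatic function definition. Both bias scenarios remain hypothetical.

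The absence of a named lead parameter and the unlisted shelf-age covariates are separate specification gaps and do not follow from this point.

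**Conclusion.** The concern holds as a matter of precision. The adjusted model for platelet hemostatic function names GCS only, although a pre-transfusion value of the same assay is planned in both arms where feasible. Some precision is given up whenever the two values are correlated. Under the stated assumptions the SE would fall by about 3% to 19%, and power would rise from about 70% to between 73% and 87%, or slightly less by simulation. Every input except the sample size, allocation and test level is assumed, and at the low end the benefit is small. The documents do not establish bias in the planned analysis. The point concerns one secondary outcome; the feasibility outcome and the GOSE power figure do not change.

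**What to change.** Under Analysis for Clinical Outcomes, add a rule for platelet-function measures:

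- Use ANCOVA of the value after the first transfusion on randomised arm, the pre-transfusion value of the same assay, and baseline GCS.
- Keep patients whose pre-value is missing. Suitable methods are pooled-mean fill with or without a missing indicator, or a constrained longitudinal model with the pre-value as an outcome. Choose one before the data are seen.
- Show the planned GCS-only model alongside.
- Report the number and percentage of missing pre-values and missing post-values by arm, so that a reader can judge which of the two models is more open to bias.

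The cost is SAP wording. No new samples or visits are needed, and clinical management is unchanged. Missing pre-values shrink the gain, and the indicator method carries the bias risk shown above if they are missing by arm and pre-value together.

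### The subgroup section promises a test of homogeneity of the treatment effect, but the only method it prescribes is a separate model within each subgroup, which yields no such test

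*Combined protocol and SAP*

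**What the plan says.** The aim is stated under Analysis for Clinical Outcomes: "Analyses to test for the homogeneity of the treatment effect will be carried out for the pre-defined subgroups". The method and its output follow at once: regression models suited to the type of outcome "will stratified by the pre-defined subgroups. Estimate of the treatment effect (odds ratio) and 95% confidence interval will be generated for each model", with the results shown on a forest plot. Neither the protocol nor the SAP text names an interaction term, a heterogeneity statistic or an interaction p-value.

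Predefined Subgroups lists five factors: craniectomy/craniotomy or not, ICP monitoring or not, arrival from the scene or from a referral hospital, aspirin or clopidogrel history, and "5) CSPs with shelf time of 1 to 7 days as compared to 8 to 14 days". The same paragraph concedes that the trial is not powered for these comparisons and says that the results "will be considered exploratory in nature and will not be used as a basis for treatment recommendations".

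**The concern.** Homogeneity means that the effect of CSP against standard care is the same in both strata. A model fitted inside one stratum asks only whether the effect there differs from zero. Two such models side by side answer two questions, and neither is the one the plan poses.

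A reader of the forest plot has to make the comparison informally, and two habits are common. Noting that one stratum is significant and the other is not finds differences too often. Waiting for two 95% intervals to separate finds them too rarely.

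Aim 1 is where this matters. It asks the pilot to identify the most suitable population for a multicenter trial, and Background and Significance says that the results will inform the choice of population and inclusion criteria. An apparent difference between scene and referral patients, or between aspirin and clopidogrel users, could steer that choice.

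**Working it through.** **Inputs from the documents.** 1:1 allocation; about 100 patients, 50 per arm; two-sided alpha 0.05; for GOS-E, "there is 80% power to detect an effect size of 0.3788", on 7 degrees of freedom.

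**Assumptions not in the documents.** Two non-overlapping strata, split 50:50 unless stated; a binary outcome with a 45% control event rate; the true odds ratio (OR) is the same in both strata.

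**1. The plan's own figure.** Noncentrality = 100 × 0.3788² = 14.35; the 5% critical value of chi-square on 7 df is 14.07; power = 0.7999. The stated 80% reproduces. It concerns the whole-sample test on eight GOS-E levels. The documents give no figure for the subgroup analyses.

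**2. What the prescribed models test.** In stratum *s*, logit(risk) = a_s + b_s × arm. The separate models test b₁ = 0 and b₂ = 0. Homogeneity is b₁ = b₂, for which the statistic is z = (b₁ − b₂)/√(SE₁² + SE₂²), or equivalently an interaction term. The plan asks for neither.

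**3. Discordance when strata are read by significance.** With stratum powers p₁ and p₂, the chance that exactly one is significant is D = p₁(1 − p₂) + p₂(1 − p₁).

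- No effect: D = 2 × 0.05 × 0.95 = 9.5%.
- Common effect with 80% overall power: overall z = 1.96 + 0.84 = 2.80. Each half-sample stratum has z = 2.80/√2 = 1.98 and power 0.508, so D = 2 × 0.508 × 0.492 = 50%. For equal strata this is the ceiling, since 2p(1 − p) cannot exceed 0.5.
- Same effect, unequal strata: 30:70 gives powers 0.335 and 0.650, D = 55%; 20:80 gives 0.240 and 0.707, D = 61%.

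**4. Smaller effects.** There are 25 patients per arm per stratum. Example at OR 0.5: treated odds = (0.45/0.55) × 0.5 = 0.409, risk 0.290. Variance of the log OR = 1/(25 × 0.45 × 0.55) + 1/(25 × 0.290 × 0.710) = 0.162 + 0.194 = 0.356. z = 0.693/0.596 = 1.16, stratum power 0.213, D = 2 × 0.213 × 0.787 = 34%.

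| Common OR | D, normal approximation | D, simulated (Wald test) | Interaction test, simulated |
|---|---|---|---|
| 1.0 | 9.5% | 7–8% | 5% |
| 0.7 | 17% | 15% | 5% |
| 0.6 | 24% | 22% | 5% |
| 0.5 | 34% | 32% | 5% |
| 0.35 | 47% | 47% | 4% |

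An uncorrected chi-square test within strata gives somewhat higher values: up to about 12% with no effect and 36% at OR 0.5. OR 0.35 has about two-thirds overall power here, so it is already a large effect.

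**5. Reading by interval overlap.** With equal standard errors, two 95% intervals separate under homogeneity with probability 2 × [1 − Φ(1.96 × √2)] = 0.6%, far below 5%.

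**6. Power of the interaction test.** Relative to the overall log OR, the standard error of the stratum difference is inflated by √(1/f + 1/(1 − f)), where f is the share in one stratum: 2.00 at 50:50, 2.18 at 30:70, 2.50 at 20:80. For a stratum difference as large as the overall effect detectable with 80% power, z = 2.80/2.00 = 1.40 and power is 29% at 50:50. It is 25% at 30:70 and 20% at 20:80.

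**7. Which listed factors can carry the test.**

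- Scene or referral arrival is fixed before randomization.
- Aspirin or clopidogrel history is also fixed before randomization, but some patients may take both (VerifyNow Measurements) and some neither (inclusion criterion b).
- Craniectomy/craniotomy and ICP monitoring are also listed under Secondary Outcomes, so they can follow from treatment.
- CSP shelf time does not exist in the standard care arm.

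**The case against.** The strongest reply is the plan's own caveat: the subgroups are declared underpowered and exploratory and are kept out of treatment recommendations, and the primary outcome is feasibility. This stands as a limit on seriousness. It does not close the gap, because it is silent on choosing the next trial's population and supplies no test.

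Second, the test is unnamed rather than excluded. For non-overlapping strata, the planned estimates and intervals would be enough to compute the z in step 2 afterwards. That is true, so a reader should not infer that the plan rules out a homogeneity test or makes one impossible. It does not specify one.

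Third, the plan never says that strata will be compared by significance or by overlap. This also stands. The discordance figures describe a likely misreading of the forest plot, not a rule in the plan.

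Fourth, the 50% figure is the maximum for equal strata and needs a large effect. The documents' 80% power belongs to a 7-df test on GOS-E, not to a binary odds ratio. The range in step 4 is the fair statement.

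Finally, the mention of an odds ratio is a small matter, since the plan already asks for models suited to the outcome.

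**Conclusion.** The concern holds as a mismatch between stated aim and stated method: a homogeneity test is promised, and only within-subgroup estimates are prescribed. If strata are compared by significance, a common effect looks different in about 7–10% of trials with no effect, about 15–32% at OR 0.7 to 0.5, and at most about 50% for a large effect. An interaction test does so in about 5% or less. This rests on two equal strata, a 45% control event rate and 50 per arm, none of the first two being given in the documents. With unequal strata and a large effect, discordance can reach 55–61%.

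A reader might infer that about half of the trial's subgroup findings will be false. The documents do not support that: it takes a large true effect and a reading rule that the plan does not state. The practical consequence is also confined to the two factors that could define a future population, arrival route and type of antiplatelet agent. The plan should be changed, but the primary feasibility outcome is not affected.

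**What to change.** For scene versus referral arrival, and for aspirin versus clopidogrel among patients who can be classified to one of the two, fit one model per factor with arm, subgroup, arm-by-subgroup interaction and baseline GCS. Beside the forest plot, report the interaction estimate (ratio of odds ratios, or the measure that fits the outcome) with its 95% CI and p-value. State that within-subgroup p-values will not be used to claim a difference.

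Label the craniectomy/craniotomy and ICP-monitoring displays as descriptive only; an interaction term would not make comparisons within post-randomization groups causal. Leave CSP shelf time to the propensity-weighted analysis already planned within the CSP arm.

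The cost is a few sentences in the SAP and one extra term per model, with no new data or patients. There is a small downside: at 100 patients the interaction test has only about 20–29% power for a difference as large as the overall effect detectable with 80% power. The plan should therefore say that a non-significant interaction is not evidence of homogeneity. The reported confidence interval will show the imprecision.

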### **Statistical Analysis Plan**

The analysis will begin by describing the baseline demographic and clinical characteristics of the overall population and then stratified by treatment arm to compare those who receive CSP and those who receive standard care. For discrete variables, proportions will be generated, and a chi-square test will be used to test for differences between the proportions. For continuous characteristics, means (medians) and standard deviations (interquartile ranges) will be calculated, and t-tests (Wilcoxon) will be used to compare the means (distributions) between treatment arms.

**Eligibility, Enrollment, and Participant Accrual:** The feasibility of enrollment will be evaluated by determining 1) the proportion of eligible patients that can be randomized, 2) the proportion of eligible patients who are enrolled in the trial, 3) proportion of enrolled patients which adherence to the study protocol, and 4) proportion of enrolled patients who complete study follow-up. These proportions will be estimated directly as the observed ratio of numbers of patients, and 95% confidence intervals will be calculated to understand the likely range of values for a larger study with a comparable research protocol and population. The reasons why patients are not enrolled including frequencies of individual exclusions and the proportion of patients declining participation or not able to be randomized will be described. Rate of participants' accrual per month with 95% C.I. will be calculated.

**Analysis for Clinical Outcomes:** The principal secondary clinical outcome for the trial will be 6-month Extended Glasgow Outcome Scale (GOS-E). The null and alternative hypothesis of the study are

H0: There is no difference in the distribution of the GOS-E scores by treatment group  
H1: There is a difference in the distribution of the GOS-E scores by treatment group

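### The 95% interval for a proportion of 0.70 at n=100 is printed with an upper limit of 0.82; the correct limit is 0.79

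*Combined protocol and SAP*

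**What the plan says.** Feasibility is the primary outcome. Under the heading Sample Size Justification and Power Analysis (n=100), the plan supports the sample size for it through the precision of estimated proportions: "we calculated the two-sided 95% CI for proportions ranging from 0.70 to 0.90". The text gives two examples. The first is that "a sample size of 100 produces a two-sided 95% CI of 0.82 to 0.95 when the sample proportion is 0.90". The second is "When the sample proportion is .70, the two-sided CI is 0.60 to 0.82".

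A table follows with columns for sample size, width, proportion, lower limit and upper limit. Its row for the full sample at 0.70 reads "100 0.19 0.700 0.60 0.82", so the 0.82 appears both in the sentence and in the table. The plan then adds "These confidence intervals are then repeated within the treatment arm", and the single-arm row at 0.70 reads "50 0.27 0.700 0.55 0.82". The interval method is not named.

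For the analysis itself, the section on eligibility, enrollment and accrual says "These proportions will be estimated directly as the observed ratio of numbers of patients", with 95% confidence intervals to be calculated around them.

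**The concern.** Three features of the n=100, P=0.70 row look wrong before any interval is computed.

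- The limits and the width disagree: 0.82 − 0.60 = 0.22, against a printed 0.19.
- The interval reaches 0.12 above the proportion and 0.10 below it. For a proportion above 0.5 the longer side should be the lower one, as it is in the other five rows.
- The upper limit equals that of the n=50 row at the same proportion, although the sample is twice as large.

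The precision table is the only sample size justification given for the primary outcome, and this is one of just two intervals quoted in the text. The plan intends such intervals to inform a larger trial, so the planning figures should be correct.

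**Working it through.** **Inputs, all from the sample size section.** Two-sided 95% level; n=100 for the full sample and n=50 per arm; proportions 0.70, 0.80 and 0.90, which give counts of 70, 80 and 90 out of 100 and 35, 40 and 45 out of 50.

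**Step 1: find the plan's method.** For x events in n, the exact limits are

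- lower = 0.025 quantile of Beta(x, n − x + 1)
- upper = 0.975 quantile of Beta(x + 1, n − x)

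| Count | Exact lower | Exact upper | Exact width | Printed limits | Printed span | Printed width |
|---|---|---|---|---|---|---|
| 70/100 | 0.6002 | 0.7876 | 0.1874 | 0.60, **0.82** | **0.22** | 0.19 |
| 80/100 | 0.7082 | 0.8733 | 0.1652 | 0.71, 0.87 | 0.16 | 0.17 |
| 90/100 | 0.8238 | 0.9510 | 0.1272 | 0.82, 0.95 | 0.13 | 0.13 |
| 35/50 | 0.5539 | 0.8214 | 0.2675 | 0.55, 0.82 | 0.27 | 0.27 |
| 40/50 | 0.6628 | 0.8997 | 0.2369 | 0.66, 0.90 | 0.24 | 0.24 |
| 45/50 | 0.7819 | 0.9667 | 0.1849 | 0.78, 0.97 | 0.19 | 0.19 |

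The exact method gives both printed limits in the last five rows. In the first row it gives the printed lower limit and the printed width, and misses only the upper limit.

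**Step 2: try other methods for 70/100 at 95%.**

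| Method | Lower | Upper |
|---|---|---|
| Wald | 0.6102 | 0.7898 |
| Wald, continuity-corrected | 0.6052 | 0.7948 |
| Wilson | 0.6042 | 0.7811 |
| Wilson, continuity-corrected | 0.5989 | 0.7855 |
| Agresti-Coull | 0.6039 | 0.7813 |
| Jeffreys | 0.6055 | 0.7832 |
| Inverted binomial test | 0.6004 | 0.7858 |

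The highest upper limit is 0.7948. Each of these methods also fails to reproduce at least one of the other five rows. For example, continuity-corrected Wilson gives 0.7741 to 0.9626 for 45/50, against the printed 0.78 to 0.97.

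**Step 3: try another confidence level.** At 99% the exact interval for 70/100 is 0.569 to 0.811. The 99% Wald upper limit, 0.818, would round to 0.82, but its lower limit is 0.582, not 0.60, and the plan states 95%.

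**Step 4: test 0.82 directly.** If the true proportion were 0.82, the probability of 70 or fewer events in 100 would be 0.0024. At an exact 95% upper limit that probability is 0.025.

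**Step 5: size of the error.**

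- Upper limit: 0.82 − 0.788 = 0.032 too high.
- Span against true width: 0.22 / 0.1874 = 1.17, so about 17% too wide.
- With the corrected limit, 0.79 − 0.60 = 0.19, which agrees with the printed width.

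**The case against.** The strongest objection is to the weight of the point, since the arithmetic is not in dispute. The interval is an illustration. The plan does not derive n=100 from it, and no feasibility threshold is set against which 0.79 or 0.82 would be judged. The error understates precision, so it does not flatter the design. The correct precision can still be read from the width of 0.19 in the same row. All of this stands, and it keeps the point minor.

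It is also fair that the table does not hide the benefit of the larger sample. At 0.70 only the upper limits coincide; the lower limits (0.60 against 0.55) and the widths (0.19 against 0.27) still show the gain.

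The width column is weaker evidence than the limits, because it follows no single rounding rule. For 80/100 the printed 0.17 matches the unrounded width (0.1652) and not the difference of the rounded limits (0.16). For 45/50 the printed 0.19 matches the rounded limits, while the unrounded width of 0.1849 rounds to 0.18. These are discrepancies of 0.01. They cannot explain 0.22 against 0.19.

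An error in reading the table from the PDF is unlikely, because the sentence carries the same 0.82.

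**Conclusion.** The upper limit of 0.82 is wrong in both places and should be 0.79. The lower limit of 0.60, the width of 0.19 and the printed limits of the other five rows are correct.

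That the plan used the exact method is inferred from those five rows, since it is not stated. The finding that 0.82 is wrong does not depend on this inference, because none of the eight methods tried exceeds 0.795 at 95%. How the slip arose is unknown. The value is correct for n=50 at 0.70, so a carry-over from that row is possible, but the document does not show it.

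This is a minor correction. It does not touch the sample size, the GOSE power statement or the planned analysis, whose intervals will be computed from the observed counts.

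**What to change.** In the sample size section, change 0.82 to 0.79 in the sentence on a proportion of 0.70 and in the n=100, P=0.700 table row. Leave the width at 0.19. The n=50 row keeps its 0.82, which is correct there. The cost is one figure corrected in two places, with no effect on sample size, conduct or analysis.

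Two optional additions would help a reader, though neither is needed for the correction:

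- Name the method as exact (Clopper-Pearson).
- State which proportions the rows describe. They apply directly to proportions of enrolled patients, such as adherence and follow-up. The per-arm rows do not apply to enrollment proportions, which are measured before arms exist. Proportions of eligible patients have a larger denominator, so the n=100 rows are slightly conservative for them. The plan gives no eligible count. Assuming 100 enrolled out of 143, 125 or 111 eligible, the exact intervals are 0.617 to 0.773, 0.719 to 0.866 and 0.830 to 0.950, and no limit moves by more than 0.017 from the exact n=100 value.
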